CHB patients regardless of HBeAg status or NUC/Interferon use history will enroll sequentially into a total of 11 open label cohorts (Cohorts 2b through 7, Cohorts 10, 11, 12, 1b and 1c). Cohorts 1b, and 1c through 5b will enroll at planned dose levels of 25 mg (Cohort 1b), 50 mg (Cohort 1c), 100 mg (Cohort 2b), 200 mg (Cohort 3b), 300 mg (Cohort 4b) and 400 mg (Cohort 5b) to receive three doses (Q28 days) of active treatment in an open label fashion. Cohort 6 will enroll CHB subjects (after Cohort 5b has completed enrollment) to receive three doses two weeks apart. Cohorts 7, 10 and 11 will enroll CHB patients sequentially (after Cohort 6 has completed enrollment) to receive three doses a week apart at increasing dose levels starting with a dose equal to Cohort 6. Cohorts 5b through 7 and Cohorts 10 and 11 will enroll sequentially (after being opened at the final planned DSC meeting) with enrollment and dosing in a later cohort not initiating until all subjects in the earlier cohort have received at least their first scheduled dose. Cohort 8 will enroll HBeAg positive treatment naïve CHB patients to receive three monthly doses of ARO-HBV. Cohort 9 will enroll HBeAg positive entecavir or tenofovir experienced CHB patients to receive three monthly doses of ARO-HBV. Cohorts 8 and 9 may enroll in parallel with Cohort 5b once opened by the DSC. Cohorts 6 through 12 will enroll at planned dose levels of 100 mg (Cohorts 6 and 7), 200 mg (Cohorts 10 and 12), and 300 mg (Cohorts 8, 9, and 11). CHB patient screening for all CHB cohorts may start when Cohort 1 opens for enrollment. However, no CHB patients may be dosed until their respective cohort is approved for dosing by the DSC (not including Cohorts 1b, 1c and 12). CHB dosing may begin and NHV dose escalation may occur based on DSC approval which can occur by vote after cumulative data through Day 8 from the current NHV cohort is available. See **Figure 1** for dose escalation schedule). CHB patients on current NUC therapy (entecavir or tenofovir) will stay on NUC therapy for the study duration. CHB patients not on NUC therapy (NUC naïve) will be started on either entecavir or tenofovir (selection between entecavir and tenofovir based on site Principal Investigator (PI) discretion) on Day 1. Either tenofovir disoproxil fumarate (including generic) or tenofovir alafenamide are acceptable.

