JNJ-6379 Treatment Reconciliation ¹²				X	X	X	X	X	X		X

* Repeat if > 2 weeks from Screening

1. Symptom-directed PEs to be performed by visit as necessary.
2. ECGs: Measured pre-dose and at 1 and 2 hours post-dose; more frequently per hour if necessary. Performed prior to other invasive procedures.
3. Cytokines Panel B: (whole blood). Venous blood samples collected pre-dose on dosing days then as indicated. Collected samples will only be analyzed at discretion of and with notification by Sponsor.
4. Vitals: Measured pre-dose and at 5 min, 0.5, 1, and 2 hours post-dose.
5. Urine pregnancy test for females of childbearing potential only. Complete pre-dose on dosing days.
6. AE/SAE data capture begins from time of informed consent.
7. Clinical Chemistry, Hematology, Coagulation and Urinalysis pre-dose only on dosing days.
8. Performed for females not of childbearing potential to confirm postmenopausal status.
9. Anti-drug antibodies collected pre-dose, Day 57 and on Day 113 or EOS.
10. If genetic testing consent is obtained, one-time whole blood sample collection will be on Day 1 or any time thereafter for SNP analysis for IFN response genes.
11. JNJ-6379 bottles (both 25 and 100 mg) should be supplied to the patient for continuous daily dosing until the next scheduled visit. On Day 1 prior to JNJ-6379 initial treatment, subject should receive dosing administration training according to the Pharmacy Manual and will be provided a patient diary for daily dose recording.
12. Patients are instructed to bring all JNJ-6379 bottles at each visit to be reconciled against the patient diary.
13. Collect plasma two-hours post-ARO-HBV dose to measure plasma concentration of ARO-HBV, JNJ-6379 and NUC (ETV or TDF).

TABLE OF CONTENTS

1	PROTOCOL SYNOPSIS	2
2	STUDY INFORMATION AND SIGNATURES	23
3	LIST OF ABBREVIATIONS AND TERMS	24
4	INTRODUCTION	26
4.1	Background Information	26
4.2	ARO-HBV and JNJ-6379 Pre-clinical Pharmacology and Toxicology Studies	27
4.3	ARO-HBV Clinical Studies	28
4.4	JNJ-6379 Clinical Studies	30
4.5	ARO-HBV and JNJ-6379 Pre-Clinical Pharmacokinetic and Product Metabolism Studies .	32
4.6	Rationale for the Study	33
4.7	Risk Assessment for Participants	34
4.8	Justification for Dose of ARO-HBV and JNJ-6379.....	36
5	OBJECTIVES	38
5.1	Primary Objectives.....	38
5.2	Secondary Objectives.....	38
5.3	Exploratory Objectives	38
6	STUDY PLAN	39
6.1	Study Design	39
6.2	Rationale for Study Design	44
6.3	Criteria for Dose-escalation and Stopping Rules	46

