The PI is responsible for the investigational product accountability, reconciliation and record maintenance at the investigational site. In accordance with all applicable regulatory requirements, the PI or designated site staff must maintain investigational product accountability records throughout the course of the study. This person will document the amount of investigational product received from Arrowhead Pharmaceuticals, Inc., the amount supplied and/or administered to and returned by participants, if applicable. A non-blinded Clinical Research Associate (CRA) will perform initial and ongoing study drug kit and placebo accountability. The non-blinded CRA will protect the integrity of the assignment blind and will not participate in data review for study participants. Used vials of ARO-HBV will be retained sequestered per participant and cohort and made available to the non-blinded CRA during study drug and placebo reconciliation, where allowable by local policy. Used bottles of JNJ-6379 will be retained sequestered per participant and made available to the CRA for study drug reconciliation.

A Drug Dispensing Log must be kept current and will contain the following information:

- the identification of the participant to whom the drug was dispensed; and
- the date(s) and quantity of the drug dispensed to the participant.

The date and time of ARO-HBV/placebo dose preparation and release will be maintained to support administration of study drug/PBO. The authorized pharmacist or qualified staff will be un-blinded to the doses. The pharmacy will dispense ARO-HBV/placebo and the study center will administer ARO-HBV only to participants included in this study following the procedures set out in the study protocol. The pharmacy will dispense JNJ-6379 to the site staff who will provide it to the patients who will take their daily dose of 250 mg (oral) at home. Patients will record taking their daily dose of JNJ-6379 on a diary provided to the clinical site. Patients will bring their used bottles of JNJ-6379 and diaries with them to each subsequent visit so that the study staff may count the remaining tablets, compare the count to the patient's recorded diary and ascertain the level of patient compliance with study treatment. Patients will be provided with additional JNJ-6379 at each visit to cover the period of time

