9.5 Study Formulation Administration

Appropriately trained employees of the clinical site will administer ARO-HBV/PBO. Each dose will be administered as a subcutaneous injection. Doses of 400 mg will be administered as two injections per dose with each injection administered into separate a site. The date, time and location of administration will be recorded in the source notes and witnessed by a second person from the clinical facility. The preferred site of injection is the abdomen. Optional additional sites are the upper arms and thighs or other sites based on PI clinical judgement.

Table 2: Injection number and volume per cohort

Cohort	Dose	Concentration	Total Injection Volume	# Injections per planned dose
1	35 mg	200 mg/mL	0.175 mL	Single
1b	25 mg	200 mg/mL	0.125 mL	Single
1c	50 mg	200 mg/mL	0.25 mL	Single
2, 2b, 6, 7	100 mg	200 mg/mL	0.5 mL	Single
3, 3b, 10, 12	200 mg	200 mg/mL	1.0 mL	Single
4, 4b, 8, 9, 11	300 mg	200 mg/mL	1.5 mL	Single
5, 5b	400 mg	200 mg/mL	2.0 mL	Two (at separate sites)

JNJ-6379 will be dispensed to patients in Cohort 12 only who will take their daily dose (250 mg oral) at home. Patients will bring all remaining tablets to their subsequent visits for compliance assessment, and receive additional tablets to cover their daily doses until the next subsequent visit.

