9.6 Timing of Treatments and Procedures

Actual times of procedures for each participant will vary depending on scheduling and will be recorded in the eCRF.

Post-dose time points will be determined based on time of injection.

In the event of multiple procedures scheduled at the same time, non-invasive procedures (i.e. ECGs, AE assessment) will be conducted prior to invasive procedures (i.e., blood sample collection). Timing of activities may be adjusted slightly to accommodate all procedures.

The following windows are allowed for study assessments/visits:

Pre-dose:	Within 60 minutes prior to dosing
PK/PD through 6 hours:	± 2 minutes
All other procedures through 6 hours:	± 10 minutes
PK/PD from 8 to 48 hours:	± 5 minutes
All other procedures from 8 to 48 hours:	± 15 minutes
Day 8:	± as per SOA
Day 15 to Day 29:	± as per SOA
Visits beyond Day 29:	± as per SOA

9.7 *Safety Endpoints*

The safety of ARO-HBV (alone or in combination with JNJ-6379) will be evaluated by collection of the following measurements performed at specified time points:

- Monitoring of AEs/ SAEs
- Physical examinations
- Vital signs
- ECG measurements
- Injection Site Reactions (Mild, Moderate or Severe): Photographic images will be taken of all injection site reactions at the time of reporting and at the time of resolution.
- Clinical laboratory tests (hematology, biochemistry, coagulation, urinalysis)
- Concomitant medications/therapy, and
- Reasons for treatment discontinuation due to toxicity

The AE/SAE reporting period for an enrolled participant will begin when the participant provides informed consent. Treatment-Emergent AEs/SAEs will be those defined as following dose administration. All AEs/SAEs that occur during the AE reporting period specified in the protocol must be reported to Arrowhead Pharmaceuticals, Inc., regardless of the relationship of the AE to study

treatment. Any known untoward event that occurs beyond the AE reporting period that the PI considers an SAE and possibly related to study treatment will be reported to Arrowhead.

9.8 *Blood Sampling for Pharmacokinetic and Pharmacodynamic Analysis*

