11.5 Pharmacokinetic Data

Plasma concentrations of ARO-HBV collected at specified time points post-dose from all participants at different dose levels will be used to calculate the following single dose pharmacokinetic parameters:

- AUC₀₋₂₄: The area under the plasma concentration versus time curve from the zero to 24 hours.
AUC_{inf}: The area under the plasma concentration versus time curve from zero to infinity.
C_{max}: The maximum plasma concentration will be obtained directly from the plasma concentration time profile.
t_{max}: The time to maximum plasma concentration will be obtained by inspection.
t_{1/2}: The half-life will be calculated by the equation $t_{1/2} = \ln(2)/k_{el}$.

The pharmacokinetic parameters will be determined using non-compartmental method(s). Descriptive statistics of pharmacokinetic parameters will include mean, standard deviation (SD), and coefficient of variation (CV), minimum and maximum. Dose-related trends in pharmacokinetic parameters will be assessed.

Plasma concentrations of ARO-HBV, NUC and JNJ-6379 will be measured at a single 2 hour post-dose time point in Cohort 12 only.

Pharmacokinetic parameters will be tabulated and summarized by dose level where applicable. The concentration-time profiles for each participant and the mean concentration-time profiles by dose level will be plotted with concentration presented on both linear and logarithmic scales. Cohort 12 CHB patient limited PK data will be evaluated separately from NHV PK data.

Statistical analysis will be performed on the pharmacokinetic parameters using validated statistical software.

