NHV cohorts will be followed for a maximum of 13 weeks from the beginning of the screening to the Day 29 EOS examination. CHB cohorts will be followed for approximately 25 weeks from screening to the Day 113 EOS examination. During the study period, safety assessments, immunologic assessments (CHB cohorts in New Zealand only), HBV virology assessments (CHB cohorts), Immunogenicity (CHB cohorts), pharmacodynamics endpoints (NHV cohorts), cytokines, complement (NHV cohorts), excretion and metabolism will be conducted as per the Schedule of Assessments in the protocol. CHB patients consenting to participate in the additional follow-up period will be followed as per Additional Follow-Up Schedule of Assessments (refer to the study protocol), every 56 days ( $\pm$  5 days) for 5 additional visits after Day 113. In addition, Cohort 12 patients will require follow-up until the Day 337 ( $\pm$  5 days).

Pharmacokinetic (PK) intensive sampling will be conducted for NHV cohorts on Day 1 (dosing day) at the time of 0 (pre-dose), 15 minutes, 0.5, 1, 2, 3, 6, 24 and 48 hours post-dose. No PK data will be sampled for CHB cohorts, except in Cohort 12 where plasma will be collected two-hours post-ARO\_HBV dose to measure plasma concentration of ARO-HBV, JNJ-6379, and NUC (ETV or TDF).

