## 9. PHARMACOKINETICS (PK)

PK analyses will be conducted with the PK Population. PK analysis of ARO-HBV concentration-time data will be performed using validated PK software (Phoenix WinNonlin version 6.3 or higher), by a standard non-compartmental model. The actual plasma sampling times from the CRF database, i.e., the elapsed time of the blood sampling time from the dosing time, will be used for PK analysis.

PK samples will be collected for NHV Cohorts 1, 2, 3 4 and 5 on Day 1 (dosing day) at the time of 0 (pre-dose), 15 minutes, 0.5, 1, 2, 3, 6, 24 and 48 hours post-dose.

Plasma concentrations of ARO-HBV, NUC and JNJ-6379 will be measured at 2 hours post-dose on Days 1, 29 and 57 in Cohort 12 only.

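### Cohort 12 JNJ-6379 and NUC levels are labelled as 2 hours post-dose, but the 2 hours run from the ARO-HBV injection and time since the oral doses is not defined

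*SAP*

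**What the plan says.** **Label.** SAP section 9 covers three drugs with one time: "Plasma concentrations of ARO-HBV, NUC and JNJ-6379 will be measured at 2 hours post-dose on Days 1, 29 and 57 in Cohort 12 only". Protocol section 11.5 does the same: "Plasma concentrations of ARO-HBV, NUC and JNJ-6379 will be measured at a single 2 hour post-dose time point in Cohort 12 only".

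**Clock.** Protocol Table 1.6, footnote 13, says which dose starts it: "Collect plasma two-hours post-ARO-HBV dose to measure plasma concentration of ARO-HBV, JNJ-6379 and NUC (ETV or TDF". SAP section 2.1 agrees ("No PK data will be sampled for CHB cohorts, except in Cohort 12 where plasma will be collected two-hours", and the sentence goes on to name the ARO-HBV dose). Protocol section 9.6 gives the general rule: "Post-dose time points will be determined based on time of injection".

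**Oral intake.** On JNJ-6379, Protocol section 9.5 says: "JNJ-6379 will be dispensed to patients in Cohort 12 only who will take their daily dose (250 mg oral) at home". Section 8.6 adds: "Patients will record taking their daily dose of JNJ-6379 on a diary provided to the clinical site". There the diary is used with a tablet count to judge compliance. NUCs are continued or started on Day 1. On tenofovir the Synopsis says: "Either tenofovir disoproxil fumarate (including generic) or tenofovir alafenamide are acceptable".

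**Records.** SAP section 8 names administration time for the ARO-HBV/placebo listing. For JNJ-6379 and NUC it promises compliance and dosing-deviation listings, and section 10.2 adds NUC dispensing. For medications generally, Protocol section 7.5 asks for indication, dose and dates.

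**Use.** SAP section 2.2.3 makes the Cohort 12 concentrations an exploratory objective. Section 9.2 plans summaries, graphs and listings, and derives no PK parameters for this cohort.

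**The concern.** A concentration is interpretable only against the time since that drug was taken. For ARO-HBV the label and the clock agree. For JNJ-6379 and NUC the label implies 2 h after intake, while the only fixed interval is from a different drug given by another route.

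SAP section 9 says PK analysis uses the time elapsed from dosing to sampling. Section 9.2 lists sampling times relative to dosing time, with deviations, for all subjects with concentration data. For the two oral drugs, no dosing time is specified from which to compute this.

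At stake is the only exposure information that this study plans for the three drugs given together. A low Day 1 JNJ-6379 value may mean only that the first tablet had not been taken. A low NUC value cannot be separated from a long interval since intake.

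**Working it through.** The plan gives no figure to reproduce. The check sizes the timing effect for JNJ-6379 from the protocol's own PK values.

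**Inputs**
- Terminal half-life 93.3 to 116 h; median tmax 1.26 to 3 h fasting and about 4 h fed (Protocol section 4.5).
- 250 mg once daily for 28 days: Cmax 13,798 ng/mL, AUC over 24 h 265,384 ng.h/mL (Protocol section 4.2, Table 1).
- NUC half-lives: not in either document.

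**Days 29 and 57**
1. k = ln 2 / half-life. Fall over 24 h = 1 − exp(−24k): 16.3% at 93.3 h and 13.4% at 116 h.
2. Fraction of steady state by Day 29 = 1 − exp(−28 × 24 × k): 99.3% and 98.2%. By Day 57 it exceeds 99.9%.
3. A one-compartment oral model (an assumption), with the absorption rate solved from tmax, gives a steady-state peak/trough ratio of 1.13 to 1.19. A sample at any time in the 24 h after the last tablet lies between about 15% below and 1% above the true 2 h value, if no doses were missed.
4. Observed exposure swings more than the model: average = 265,384 / 24 = 11,058 ng/mL, and Cmax / average = 13,798 / 11,058 = 1.25. This compares peak with average, not with trough, so 25% is a guide and not a strict bound.

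Taken together, the timing effect is about 15 to 25%.

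**Day 1**
1. First tablet after the draw: the level is 0.
2. First tablet 0.25 to 2 h before the draw: the same model gives 29% to 100% of the first-dose peak across the tmax range.
3. Size of that peak: with linear superposition near steady state, it is at least Cmax minus trough. Trough cannot exceed the average, so the peak is at least 13,798 − 11,058 = 2,740 ng/mL.
4. Dividing Cmax by the elimination-only accumulation factor, 1 / (1 − exp(−24k)) = 6.12 to 7.48, would give 2,253 to 1,843 ng/mL. That is below the floor in step 3, so it should not be used.

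If the SAP section 9.2 rule for values below quantitation were applied to JNJ-6379, a sample drawn before the first tablet would enter the arithmetic mean as 0.

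**NUC.** No calculation is possible from the documents.

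**The case against.** The strongest reply is that the label is only loose. Table 1.6 and SAP section 2.1 both name the ARO-HBV dose, and nowhere is the sample said to be 2 h after JNJ-6379 or NUC. That stands: a careful reader can recover the correct meaning. It does not supply the missing interval for the oral drugs.

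Three stronger readings are tempting, and the documents do not support them.
- *Intake times were not recorded.* This would be an inference from silence. A JNJ-6379 diary exists, its fields and the Pharmacy Manual are not in the documents, and the SAP expects some NUC compliance data. What can be shown is that no recording of clock time is specified.
- *The concentrations are uninterpretable.* This fails for JNJ-6379 on Days 29 and 57, given the long half-life. Tablet counts against the diary also help to identify missed doses.
- *NUC results will be averaged across molecules.* This would rest on the single word Nucleos(t)ide in the title of SAP Table 14.2.3.1 and the figures. ARO-HBV also has one title, yet SAP section 9.2 presents its two analytes separately. Footnote 13 names ETV or TDF; tenofovir alafenamide is permitted for CHB patients generally, and nothing shows that a Cohort 12 patient took it. The gap is that no split by molecule is stated.

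It is also fair to say that the remedy comes late. SAP section 17.2 reports an interim analysis of data to Day 113 for all cohorts, with a cut-off of 14 November 2019, so the samples appear to predate protocol version 6.0 and this SAP. Retrieval is then more realistic than new capture.

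**Conclusion.** The point holds in limited form. The Cohort 12 JNJ-6379 and NUC concentrations are timed from the ARO-HBV injection, and neither document defines or specifies recording time since the last oral dose. They therefore cannot be read as 2 h after JNJ-6379 or NUC.

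The consequence is greatest for Day 1 JNJ-6379, where the summary can mix samples drawn before and after the first tablet: zero against up to a full first-dose peak. Whether it does mix them is not known. For NUC the consequence is real but unquantified. For JNJ-6379 on Days 29 and 57 it is modest.

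The steady-state figure assumes daily dosing without missed doses and, at its lower end, a one-compartment model. The Day 1 floor assumes linear superposition. The consequence is confined to an exploratory, descriptive output: no PK parameters, safety results or ARO-HBV concentrations depend on it.

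**What to change.** - In SAP section 9, Table 14.2.3.1 and the Cohort 12 concentration figures, label the JNJ-6379 and NUC results '2 h after ARO-HBV injection'.
- Capture the date and clock time of the last JNJ-6379 and NUC intake before each Day 1, 29 and 57 sample or, if sampling is complete, retrieve them from diaries or source. List each concentration with the time since that intake.
- Flag Day 1 JNJ-6379 samples drawn before the first tablet and exclude them from the Day 1 mean.
- State that NUC concentrations are summarised separately by molecule.

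The cost is a small capture or retrieval effort for 12 patients at three visits, with no extra samples. If the times cannot be retrieved, only the relabelling and the summary by molecule remain possible.

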### 9.1 Definition of variables

Whenever possible, the PK parameters listed below will be calculated for each subject based on the plasma concentrations of ARO-HBV according to the model independent approach, at Day 1.

Parameter	Description
AUC 0-24	The area under the plasma concentration-time curve, from time 0 (time of dosing) to 24 hours post dose, i.e., partial AUC, calculated by the log-linear trapezoidal method. AUCs for other time period could also be calculated in the analysis time.
AUC 0-inf	The area under the plasma concentration-time curve from time 0 extrapolated to infinity. AUC 0-inf is calculated as the sum of AUC 0-t plus the ratio of the last measurable plasma concentration to the elimination rate constant ( $\lambda_z$ ).
AUC 0-t	The area under the plasma concentration-time curve, from time 0 (time of dosing) to the last time point with measurable analyte concentration, calculated by the log-linear trapezoidal method.
C max	Maximum observed concentration.
T max	The first time when C max is observed
t ½	Apparent terminal elimination half-life of medication, calculated as 0.693/ $\lambda_z$ .
$\lambda_z$ :	The apparent first-order terminal elimination rate constant, calculated by linear least-squares regression analysis the terminal log-linear phase of the plasma concentration vs. time curves using at least 3 time points.
DN_AUC 0-24	Dose-normalized AUC 0-14d , calculated as AUC 0-t divided by dose

Parameter	Description
DN_AUC 0-inf	Dose-normalized AUC 0-inf , calculated as AUC 0-inf divided by dose
DN_AUC 0-t	Dose-normalized AUC 0-t , calculated as AUC 0-t divided by dose
DN_C max	Dose-normalized C max , calculated as C max divided by dose

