## 9.2 Biostatistical methods

The two ARO-HBV analytes, JNJ 73763976 (AD04872) and JNJ 73763924 (AD05070) will be analyzed and presented separately (as appropriate).

ARO-HBV plasma concentrations will be listed by subject, dose level/treatment, and nominal (scheduled) sampling time. ARO-HBV concentrations will be summarized by dose level/treatment and nominal sampling time for the PK Analysis Population. Plasma concentrations that are below the limit of quantitation (BLQ) will be set to 0 for calculation of summary statistics for concentration data at each time point, except geometric statistics (geometric mean and geometric CV%). For the calculation of the geometric statistics they will be treated as equal to the Lower Limit of Quantification (LLQ). Missing values will be omitted from the calculation of descriptive statistics.

The actual blood sampling dates and times relative to dosing time will be listed by study group (dose level/treatment), subject and nominal sampling time, with time deviation calculated, for all subjects with available plasma concentration data, including subjects receiving placebo or subjects excluded from the PK Analysis Population.

Figures of individual plasma concentration vs. actual time profiles for ARO-HBV will be produced on both linear and semi-log scales for the PK Analysis Population. Mean and median plasma blood concentration vs. nominal time curves for all dose levels/treatments in the PK Analysis Population will be plotted together on both linear and semi-log scales for ARO-HBV.

Pharmacokinetic parameters for each dose level will be calculated from the concentrations of ARO-HBV measured in pre-dose and post-dose plasma samples. For the calculation of the PK parameters, all plasma concentrations that are BLQ prior to the first measurable concentration will be set to zero. The BLQ values that are between measurable concentrations will be set to missing. The BLQ values that occur at the end of the profile (after the last quantifiable concentration) will be set to missing and will not be used for the estimation of parameter values. Dose normalized PK parameters (DN\_AUC0-24, DN\_AUC0-inf, DN\_AUC0-t, and DN\_Cmax) will be calculated as well.

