## 21. FIGURES

PK Figures will be produced for NHV cohorts (Cohorts 1, 2, 3, 4 and 5). Others will be produced separately for NHV cohorts (Cohorts 1, 2, 3, 4 and 5), CHB cohorts (Cohorts 1b, 1c, 2b, 3b, 4b, 5b, 6, 7, 8, 9, 10,11 and 12), *and the subset of CHB patients that participated in the follow up period.*

No.	Title	Analysis Population	Day 113: Interim Analysis
14.2.1.1.1a	Mean (+/-SD) Plasma Concentrations of ARO-HBV versus Time by Dose (Linear Scale)	PK	X
14.2.1.1.1b	Mean (+/-SD) Plasma Concentrations of ARO-HBV versus Time by Dose (Semilogarithmic Scale)	PK	X
14.2.1.2.1a	Median Plasma Concentrations of ARO-HBV versus Time by Dose (Linear Scale)	PK	X
14.2.1.2.1b	Median Plasma Concentrations of ARO-HBV versus Time by Dose (Semilogarithmic Scale)	PK	X
14.2.2.1.1a	Individual Plasma Concentrations of ARO-HBV versus Time (Linear Scale)	PK	X
14.2.2.1.1b	Individual Plasma Concentrations of ARO-HBV versus Time (Semilogarithmic Scale)	PK	X
14.2.1.1.2a	Mean (+/-SD) Plasma Concentrations of ARO-HBV, Nucleos(t)ide and JNJ-6397 versus Time by Dose (Linear Scale) (Cohort 12) [CHB Cohort 12 only]	PK	X
14.2.1.1.2b	Mean (+/-SD) Plasma Concentrations of ARO-HBV, Nucleos(t)ide and JNJ-6397 versus Time by Dose (Semilogarithmic Scale) (Cohort 12) [CHB Cohort 12 only]	PK	X
14.2.1.2.2a	Median Plasma Concentrations of ARO-HBV, Nucleos(t)ide and JNJ-6397 versus Time by Dose (Linear Scale) (Cohort 12) [CHB Cohort 12 only]	PK	X
14.2.1.2.2b	Median Plasma Concentrations of ARO-HBV, Nucleos(t)ide and JNJ-6397 versus Time by Dose (Semilogarithmic Scale) (Cohort 12) [CHB Cohort 12 only]	PK	X
14.2.2.1.2a	Individual Plasma Concentrations of ARO-HBV, Nucleos(t)ide and JNJ-6397 versus Time (Linear Scale)	PK	X
14.2.2.1.2b	Individual Plasma Concentrations of ARO-HBV, Nucleos(t)ide and JNJ-6397 versus Time (Semilogarithmic Scale) (Cohort 12) [CHB Cohort 12 only]	PK	X
14.2.3.1	Scatterplot of Individual and Mean Plasma AUC 0-24 versus Dose for ARO-HBV	PK	X
14.2.3.2	Scatterplot of Individual and Mean Plasma AUC 0-inf versus Dose for ARO-HBV	PK	X
14.2.3.3	Scatterplot of Individual and Mean Plasma AUC 0-t versus Dose for ARO-HBV	PK	X
14.2.3.4	Scatterplot of Individual and Mean Plasma C max versus Dose for ARO-HBV	PK	X

No.	Title	Analysis Population	Day 113: Interim Analysis
14.2.4.1	Scatterplot of Individual and Mean Plasma Dose Normalized AUC 0-24 versus Dose for ARO-HBV	PK	X

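### SAP 9.1 gives DN_AUC0-24 the formula of DN_AUC0-t and an impossible 0-14d label; the row is wrong as written, with limited effect

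*SAP*

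**What the plan says.** The parameter table in SAP 9.1 defines two AUCs that matter here. AUC0-24 runs from dosing "to 24 hours post dose, i.e., partial AUC, calculated by the log-linear trapezoidal method". AUC0-t runs from dosing "to the last time point with measurable analyte concentration, calculated by the log-linear trapezoidal method". The first has a fixed end; the second ends wherever the assay stops detecting drug.

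The same table has four dose-normalized rows. The row named DN_AUC0-24 is described as "Dose-normalized AUC 0-14d , calculated as AUC 0-t divided by dose". The row named DN_AUC0-t is described as "Dose-normalized AUC 0-t , calculated as AUC 0-t divided by dose". For comparison, DN_AUC0-inf is "Dose-normalized AUC 0-inf , calculated as AUC 0-inf divided by dose", and DN_Cmax is Cmax over dose.

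Volunteers are sampled at "0 (pre-dose), 15 minutes, 0.5, 1, 2, 3, 6, 24 and 48 hours post-dose" (SAP 2.1, repeated in SAP 9). SAP 9.2 lists four "Dose normalized PK parameters" to be calculated, with DN_AUC0-24 and DN_AUC0-t as separate items. SAP 21 gives each its own figure, 14.2.4.1 for 0-24 and 14.2.4.3 for 0-t; both titles begin "Scatterplot of Individual and Mean Plasma Dose Normalized AUC".

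**The concern.** The name of the parameter, its description and its formula point to three different quantities: a 0-24 h AUC, a 0-14 day AUC and an AUC to the last measurable sample. Nothing else in the SAP corrects the row.

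The quantity that would be lost is the fixed-window one. AUC0-t covers a period that can differ between subjects and, because higher concentrations stay above the assay limit for longer, is likely to lengthen with dose. Plotted against dose under a 0-24 name, it could show a trend that partly reflects assay sensitivity. Single-dose PK in volunteers is a secondary objective, so the definition should be right even though these plots are descriptive.

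**Working it through.** **1. Formulas side by side (SAP 9.1).**

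| Parameter name | AUC or Cmax in the description | Numerator in the formula | Match? |
|---|---|---|---|
| DN_AUC0-24 | AUC0-14d | AUC0-t | no |
| DN_AUC0-inf | AUC0-inf | AUC0-inf | yes |
| DN_AUC0-t | AUC0-t | AUC0-t | yes |
| DN_Cmax | Cmax | Cmax | yes |

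As written, DN_AUC0-24 = AUC0-t / dose = DN_AUC0-t. This identity holds for each of the 5 × 4 = 20 planned active volunteers and for both analytes. Figures 14.2.4.1 and 14.2.4.3 would therefore carry the same points.

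**2. The label.** The last scheduled sample is at 48 h, which is 2 days. No 0-14 day AUC can be formed, and none is defined elsewhere in the SAP.

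**3. When the written value differs from the intended one.** The ratio of written to intended value is (AUC0-t / dose) / (AUC0-24 / dose) = AUC0-t / AUC0-24; dose cancels.

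- Last measurable sample at 24 h: the two AUCs cover the same interval and the ratio is 1.
- Last measurable sample at 48 h: the 24-48 h area is added and the ratio exceeds 1.
- Last measurable sample before 24 h: the SAP does not give a clean comparison (see the objection).

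**4. Size for a last sample at 48 h.** The documents give no ARO-HBV half-life or absorption rate, so these are assumptions. I used a one-compartment model with first-order absorption, the SAP sampling times, and trapezoids that are linear on the rise and logarithmic on the decline. AUC0-48 / AUC0-24 is:

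| Assumed half-life | ka 0.3/h | ka 0.5/h | ka 1.0/h |
|---|---|---|---|
| 3 h | 1.016 | 1.008 | 1.005 |
| 6 h | 1.114 | 1.086 | 1.072 |
| 16 h | 1.485 | 1.419 | 1.381 |

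The overstatement is thus about 0.5 to 11% for half-lives of 3 to 6 h, and 38 to 48% at 16 h. Protocol 4.5 expects ARO-HBV to become unmeasurable in the circulation within 1 to 2 days. That is compatible with a last measurable sample at 24 h, and does not settle whether it falls there, earlier or later.

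**5. What the row feeds.** SAP 9.2 tests dose proportionality by regressing the log of un-normalized AUC0-24, AUC0-t and Cmax on log dose. No dose-normalized parameter enters that model. Un-normalized AUC0-24 is summarized by dose level and has its own scatterplot (Figure 14.2.3.1).

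**The case against.** The strongest reply is that the intent is plain. The parameter is named 0-24, the other three rows divide the named quantity by dose, SAP 9.2 lists the two parameters separately, and the figures have separate titles. The 14-day label looks like leftover template text, and a careful programmer would probably have divided AUC0-24 by dose. Each volunteer cohort also has a single dose, so a cohort's AUC0-24 summary divided by 35, 100, 200, 300 or 400 recovers the missing quantity. All of this stands and limits the consequence. It does not make the row correct: the formula is explicit and contradicts the name.

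A reader might infer three stronger things that the documents do not support.

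- *That the dose-proportionality conclusion is compromised.* It is not; the regression uses un-normalized parameters.
- *That every one of the 20 active volunteers gets a wrong number.* The duplication would apply to all of them, but the value is unchanged wherever the last measurable sample is at 24 h.
- *That the parameter is understated by a third to two thirds when drug is last measurable at 6 h.* Under the 3 to 6 h half-life assumptions, AUC0-6 / AUC0-24 does come out at 0.34 to 0.68. That ratio, however, uses a numeric 24 h concentration from the model. SAP 9.2 sets values below quantitation after the last measurable sample to missing and bars them from parameter estimation. Such a subject has no usable 24 h value, and the SAP does not say how AUC0-24 would then be obtained. The ratio therefore does not measure the gap between the written and corrected formulas under this plan.

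**Conclusion.** The definition is wrong as written: the description names an AUC that 48 h sampling cannot yield, and the formula belongs to another parameter. Followed literally, it makes DN_AUC0-24 a copy of DN_AUC0-t, and AUC0-24 / dose is not produced.

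This is a minor correction. The numerical effect is nil for a last measurable sample at 24 h. For one at 48 h it is roughly 0.5 to 11% under half-lives of 3 to 6 h, rising to about 50% at 16 h; these figures rest entirely on assumed kinetics. The effect is confined to descriptive dose-normalized PK outputs.

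Figure 14.2.4.1 is marked for the Day 113 interim analysis, so one might suppose that an erroneous plot has already been delivered. The documents do not show how it was programmed, so this is something to check rather than a finding.

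**What to change.** Replace the row in SAP 9.1 with: DN_AUC0-24, dose-normalized AUC0-24, calculated as AUC0-24 divided by dose. Delete the reference to AUC0-14d.

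Then check how Figure 14.2.4.1 was derived, together with any DN_AUC0-24 entries in Table 14.2.2.1 and Listing 16.2.6.2. The SAP gives only titles for the table and listing, so whether they carry the parameter has to be confirmed. Re-run whatever was programmed from the current text.

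The cost is one line of SAP wording and, at most, a re-run of one derived variable and its outputs. There is no scientific trade-off.
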